## 2.2 Secondary Objectives

- To evaluate the sensitivity, specificity, positive and negative predictive value of CEM compared to LE CEM images (FFDM equivalent), DBT and ultrasound for the detection of additional malignant lesions in the ipsilateral and contralateral breast.
- To evaluate the difference of the index cancer size estimation among CEM, LE images, DBT, and ultrasound compared to pathology measurements as the ground truth.
- To evaluate the incremental cancer detection rate provided by CEM, DBT, and US compared to the OSF diagnosis.
- 2.3 Exploratory Objectives
  - To evaluate the rate of referral to breast MRI in the study cohort.
  - To evaluate the performance of MRI for breast cancer diagnosis and compare it with other imaging modalities of CEM, LE images, DBT and ultrasound.
  - To evaluate the feasibility of CEM-guided biopsy of CEMonly detected lesions. The technical success of CEM guided biopsies will be determined by the fraction of biopsies that achieve adequate sampling of the target.

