# 4.0 Study Endpoints\*

4.1 Primary study endpoint:

Accuracy of CEM for incremental cancer detection in the ipsilateral and contralateral breasts. For the purpose of the study, up to 4 additional biopsy sites will be included in the analysis.

[figure not shown]
- 4.2 Secondary study endpoints:
  - Sensitivity, specificity, positive and negative predictive value of CEM, LE images, DBT, and ultrasound compared to pathology measurements as the ground truth.
  - The difference of the largest measurement of the index cancer on *LE*, *CEM*, *DBT* and *US* compared to pathology.
  - Incremental cancer detection rate provided by CEM, DBT and US.
- 4.3 Exploratory Endpoints:
  - *Rate of breast MRI utilization and the corresponding diagnosis in the study cohort.*
  - *The fraction of CEM biopsies that achieve adequate sampling of the target.*

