## 5.4 *CEM-guided biopsies:*

CEM- guided biopsy device uses a stereotactic technique to target areas of abnormal enhancement in the breast. The first commercially available CEM-guided biopsy device (GE Healthcare Serena BrightTM CEM biopsy system) has been U.S. Food & Drug Administration 510(k) cleared in May 2020. This system is capable of both conventional stereotactic and CEMguided biopsies. For both methods the system uses angular mammographic acquisitions in the breast to calculate the target, but for stereotactic biopsies it uses the morphologic abnormality in the breast as the target, whereas for CEM-guided biopsies it uses the area of suspicious enhancement as the target. With the exception of targeting, the biopsy procedure and the biopsy needles used for the procedure are identical for both methods (Appendix A).

For those study patients who demonstrate abnormal CEM enhancement with no correlate on FFDM or US, GE Healthcare Serena BrightTM CEM biopsy system will be used to perform CEM- guided biopsies. CEMguided biopsies may also be utilized for choosing the areas of most prominent CEM enhancement as biopsy targets for extensive mammographic abnormalities, where precise targeting is difficult. The presence of distinct abnormal enhancement within a target is expected to correlate with the most metabolically active areas of the lesion [31]. This may improve the accuracy of biopsy and decrease the rate of upgrade to malignancy at surgery.

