## 15.0 Data Management\* and Confidentiality

### 15.1 Statistical considerations

The primary objective of this study is to compare the accuracy of CEM and LE images (FFDM equivalent) for the detection of additional cancer sites in the affected breast and in the contralateral breast among patients with known BC diagnosed or highly suspicious at an outside facility and presenting to MD Anderson for staging imaging. The images of CEM/LE and DBT for each patient will be read/reviewed by 5 radiologists, and the majority agreement among 5 radiologists on the lexicon and BI-RADS assessment will be used for consensus. If all 5 radiologists disagree, then a consensus conference will be held. Pathology results will be considered the ground truth. Breast tissue lesions will be categorized as positive if determined as invasive cancer or DCIS, and otherwise will be categorized as negative that includes the lesions of uncertain malignant potential without subsequent surgical upgrade to invasive cancer or DCIS.

The primary outcome of this study is accuracy determined by comparing the CEM/LE results to that of the pathologic evaluations. Specifically, it is defined as the number of concordant cases between CEM/LE and pathologic evaluation divided by the total sample size. Secondary outcomes include sensitivity, specificity, negative predictive value (NPV) and positive predictive value (PPV). Sensitivity (specificity) is defined as the number of correctly diagnosed positive (negative) cases divided by the total number of confirmed positive (negative) cases, NPV is defined as the number of true negative lesions obtained from CEM/LE divided by the corresponding total predicted number of negative lesions. The PPV is similarly defined for positive breast lesions. Cancer detection rate is defined as number of invasive malignancy or DCIS divided by the total sample size.

A successful CEM guided biopsy is defined as a biopsy which successfully sampled the abnormality in question. This procedure will be considered feasible if 95% patients or more have successful CEM guided biopsy among those who will undergo this procedure, which is similar to the success rate of the prone stereotactic vacuum assisted biopsies [41].

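### The 95% feasibility rule pools all CEM-guided biopsies, although the objective is limited to CEM-only lesions, so the rule does not measure the objective; the error can run either way

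*Combined protocol and SAP*

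**What the plan says.** Section 2.3 (repeated in the Study Summary) sets the exploratory objective: "To evaluate the feasibility of CEM-guided biopsy of CEMonly detected lesions". The same bullet says that technical success will be judged by the share of biopsies with adequate sampling.

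Section 5.4 gives two indications for the procedure. The first is CEM-only disease: "For those study patients who demonstrate abnormal CEM enhancement with no correlate on FFDM or US". The second is optional. Here CEM guidance serves to pick out strongly enhancing spots "as biopsy targets for extensive mammographic abnormalities, where precise targeting is difficult". Targets of the second kind are visible on mammography, so they are not CEM-only.

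Section 4.3 states the endpoint without limiting it to either group: "The fraction of CEM biopsies that achieve adequate sampling of the target". Section 5.5 uses the same per-biopsy fraction.

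Section 15.1 defines success ("A successful CEM guided biopsy is defined as a biopsy which successfully sampled the abnormality in question") and then sets the decision rule: "This procedure will be considered feasible if 95% patients or more have successful CEM guided biopsy among those who will undergo this procedure". It ties the threshold to the success rate of prone stereotactic vacuum-assisted biopsy.

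**The concern.** The objective names one group of lesions, the procedure is open to two, and the rule counts both. No section limits the denominator to CEM-only lesions or asks for results by indication. The biopsy data listed under image-guided biopsies in section 5.3 (cores, gauge, adequacy, concordance) do not include the indication, so the split may have to be reconstructed afterwards.

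At stake is what a declaration of feasibility would mean. Sections 3.3 and 14.3 describe the benefit as direct biopsy of CEM-only lesions without MRI. A pooled rate could declare that feasible when CEM-only lesions miss the plan's own threshold, or infeasible when they meet it.

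The unit is a second, smaller mismatch. Section 15.1 counts patients, while 2.3, 4.3 and 5.5 count biopsies.

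**Working it through.** **Inputs.** The 95% threshold is declared in 15.1, so there is no calculation to reproduce. The documents do not give the number of CEM-guided biopsies, the share that are CEM-only, or success by type of target. All of these are assumed below.

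**Formula.** Let s be the CEM-only share, p the CEM-only success rate and q the success rate for the other targets. The pooled rate is s·p + (1 − s)·q. It equals p only if p = q or s = 1.

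**1. Others do better (false pass).** 9/10 CEM-only (90%, fails) plus 20/20 others gives 29/30 = 96.7%, which passes. More generally, the lowest CEM-only rate that still gives a pooled 95% is (0.95 − (1 − s)·q)/s:

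| CEM-only share s | q = 100% | q = 98% |
|---|---|---|
| 70% | 92.9% | 93.7% |
| 50% | 90.0% | 92.0% |
| 30% | 83.3% | 88.0% |
| 20% | 75.0% | 83.0% |

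For example, at s = 30% and q = 100%: (0.95 − 0.70)/0.30 = 83.3%.

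**2. Others do worse (false fail).** With CEM-only at 97%, the pooled rate is:

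| CEM-only share s | q = 85% | q = 90% |
|---|---|---|
| 30% | 88.6% | 92.1% |
| 50% | 91.0% | 93.5% |
| 70% | 93.4% | 94.9% |

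For example, 0.30 × 0.97 + 0.70 × 0.85 = 0.291 + 0.595 = 88.6%. Every cell is below 95%, although CEM-only lesions pass.

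**3. Equal success.** If p = q, the pooled rate is p and there is no bias.

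**4. Chance of meeting the rule.** Assume 20 biopsied patients, so 0.95 × 20 = 19 successes are needed, and a true CEM-only success of 85%. Exact binomial probabilities:

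| CEM-only / other | q = 85% | q = 98% | q = 100% |
|---|---|---|---|
| 20 / 0 | 0.176 | 0.176 | 0.176 |
| 10 / 10 | 0.176 | 0.478 | 0.544 |
| 6 / 14 | 0.176 | 0.666 | 0.776 |

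The first row is the question the objective asks. For 10/10 with q = 100%, at least 9 of the 10 CEM-only biopsies must succeed: 10 × 0.85⁹ × 0.15 + 0.85¹⁰ = 0.347 + 0.197 = 0.544.

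**The case against.** **The scope may be implied.** In 2.3 the success fraction directly follows the CEM-only wording, so 4.3 and 15.1 could be shorthand for that objective. This is a fair reading of intent. But 15.1 states its own denominator, everyone who undergoes the procedure, and an analyst following it would pool.

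**The bias is not shown to flatter.** A reader might infer that mammographically visible targets are easier and will carry the rule. The documents do not support that. Section 5.4 describes these targets as hard to target precisely. It says that a CEM-guided procedure aims at the enhancing area, without distinguishing the indications. Section 5.5 provides a marker and a post-procedure mammogram for all biopsy methods, and post-procedure CEM images after CEM-guided biopsy for pathologic enhancement, so sampling of CEM-only lesions can also be checked. A large lesion might more easily satisfy the broad success definition in 15.1, but that is inference. This objection stands: the direction is open.

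**Cancelled procedures.** A reader might also infer that a woman whose target fails to enhance again drops out of the denominator. The plan does not say so. Section 8.1 includes contrast administration for the biopsy as part of participation, and whether an injected but unsampled patient has undergone the procedure is undefined.

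**The reach is small.** The endpoint is exploratory, and the Study Summary foresees one CEM-guided biopsy per participant, which limits the effect of the unit mismatch. Both points stand, and both limit the weight of the finding. They do not remove it, because the plan attaches a pass/fail declaration to this endpoint.

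**Conclusion.** The mismatch is on the face of the text: the objective covers CEM-only lesions, and the rule covers all patients who have the procedure. The rule as written therefore answers a different question from the objective.

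The size and sign of the error depend on quantities that the plan does not give. Under the assumed mixes, a pooled pass is compatible with CEM-only success as low as 75.0% (share 20%, others 100%), and a pooled fail with CEM-only success of 97%. Equal success rates give no error. The finding does not rest on either group being easier to sample.

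This is a correction to one exploratory endpoint. The primary and secondary analyses are unaffected.

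**What to change.** In 4.3 and 15.1:

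- Apply the 95% rule only to CEM-guided biopsies of lesions recorded before the procedure as having no correlate on FFDM or ultrasound.
- Report CEM-guided biopsies of extensive mammographic abnormalities separately, outside the rule.
- Use one unit, patient or biopsy, in 2.3, 4.3, 5.5 and 15.1.
- Give an exact confidence interval with the observed fraction.
- State whether a patient injected with contrast for the biopsy but not sampled counts as having undergone the procedure. Counting her as a failure moves the measure from technical success among biopsies to completion of the procedure, so the choice should be explicit.

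This changes only what is counted. It costs a few sentences and one indication field on the biopsy form.

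The drawback is a smaller denominator. For illustration, if every biopsy succeeds, the exact two-sided 95% lower limit is 0.025^(1/n): 88.4% for 30/30 but 69.2% for 10/10. With fewer than 20 CEM-only biopsies a single failure misses the threshold (18/19 = 94.7%), so the interval should be read alongside the pass/fail result.

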| Study Population   | 
 
Female patients with known invasive or in-situ breast cancer diagnosed at an outside facility and presenting to MD Anderson for staging with imaging.
 
Female patients referred from outside institutions with imaging findings categorized as highly suspicious (BI-RADS 5 or 4C) on outside imaging or on re-review by MD Anderson's radiologists, and referred for staging at MDACC.
 
 |  |  |
| Sample Size  | 83  |  |  |
| Study Duration for
individual
participants                         | One diagnostic CEM imaging examination
In addition, if indicated, one CEM-guided biopsy  |  |  |

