5.5 Biopsy markers and post-procedure mammograms

For all biopsy methods a biopsy marker will be placed at the target as the standard of care [32]. As a part of the standard of care we will perform a post-procedure mammogram after tissue sampling and clip placement [32].

For those patients who undergo CEM-guided biopsies for pathologic enhancement, post-procedure CEM images of the biopsied breast will be obtained.

The technical success of CEM guided biopsies will be determined by the fraction of biopsies that achieve adequate sampling of the target.

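### The 95% feasibility rule for CEM-guided biopsy (Section 15.1) has no planned number of procedures and no confidence interval, so its pass/fail verdict would be poorly supported

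*Combined protocol and SAP*

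**What the plan says.** Feasibility of CEM-guided biopsy is an exploratory objective (Sections 1.0 and 2.3). Section 15.1 first defines success for a single procedure: "A successful CEM guided biopsy is defined as a biopsy which successfully sampled the abnormality in question". It then sets the decision rule: "This procedure will be considered feasible if 95% patients or more have successful CEM guided biopsy among those who will undergo this procedure". It supports the 95% figure by likeness to prone stereotactic vacuum-assisted biopsy, citing reference 41.

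Elsewhere the measure is a proportion of biopsies. The exploratory endpoint in Section 4.3 is "The fraction of CEM biopsies that achieve adequate sampling of the target", and Sections 2.3 and 5.5 agree with it.

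The number of procedures is left open. Section 5.4 assigns CEM-guided biopsy as follows: "For those study patients who demonstrate abnormal CEM enhancement with no correlate on FFDM or US". It also permits the technique for extensive mammographic abnormalities that are hard to target. The study summary in Section 1.0 foresees, per participant: "In addition, if indicated, one CEM-guided biopsy". The 83 patients are justified in Section 15.2 for the CEM versus FFDM accuracy comparison only. Section 15.3 names the outcomes to be estimated with 95% confidence intervals, and biopsy success is not among them.

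**The concern.** A rule that turns a proportion into a verdict needs a denominator, or an interval, before its error rates are known. This one has neither. The denominator is whatever subset of the 83 patients comes to CEM-guided biopsy. The cut-off also sits at about the success rate of the technique used as the yardstick, so a procedure that only matches the yardstick has no margin.

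At stake is a statement of feasible or not feasible that readers may use. Section 14.3 presents direct biopsy of CEM-only lesions, without MRI or MRI-guided biopsy, as a potential benefit. A negative label after one failed procedure, or a positive one after a handful of successes, would say more than the data can.

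**Working it through.** The plan states no power, error rate or number of procedures for this endpoint, so there is no figure of its own to reproduce. The check is of how the rule behaves.

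**Inputs from the documents.** Cut-off 95% (Section 15.1); at most 83 patients (Sections 10.1 and 15.2).

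**Assumptions.** The rule is applied to the observed proportion, since no test or bound is given. There is one independent procedure per patient. The number of procedures n and the true success rate p are not given, so both are shown as ranges.

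**Formulas.** The smallest passing count is r = 0.95n rounded up to a whole number. The chance of passing is P(X ≥ r) with X binomial (n, p). The last column is the two-sided 95% Clopper-Pearson lower limit when exactly r of n succeed; when r = n it equals 0.025^(1/n).

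**Zero-failure zone.** One failure leaves (n−1)/n, which reaches 0.95 only when n ≥ 20. So for n ≤ 19 any single failure fails the rule.

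**Worked cases**
- n=10, p=0.95: r=10; pass = 0.95^10 = 0.599; miss = 0.401.
- n=19, p=0.95: 0.95 × 19 = 18.05, so r=19; pass = 0.95^19 = 0.377; miss = 0.623.
- n=20, p=0.95: r=19; pass = 0.95^20 + 20 × 0.05 × 0.95^19 = 0.358 + 0.377 = 0.736 (before rounding of the terms); miss = 0.264.
- n=10, p=0.80: pass = 0.80^10 = 0.107.
- 10 of 10 successes: lower limit = 0.025^(1/10) = 0.692.

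**Chance of passing, by true success rate**

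| n | r | p=0.80 | p=0.90 | p=0.95 | p=0.98 | p=0.99 | Lower limit at r of n |
|---|---|---|---|---|---|---|---|
| 5 | 5 | 0.328 | 0.590 | 0.774 | 0.904 | 0.951 | 47.8% |
| 10 | 10 | 0.107 | 0.349 | 0.599 | 0.817 | 0.904 | 69.2% |
| 19 | 19 | 0.014 | 0.135 | 0.377 | 0.681 | 0.826 | 82.4% |
| 20 | 19 | 0.069 | 0.392 | 0.736 | 0.940 | 0.983 | 75.1% |
| 30 | 29 | 0.011 | 0.184 | 0.554 | 0.879 | 0.964 | 82.8% |
| 83 | 79 | <0.001 | 0.073 | 0.599 | 0.974 | 0.998 | 88.1% |

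**Reading the table**
- At a true 95%, the chance of missing the rule is 23%, 40%, 62%, 26%, 45% and 40% down the rows. It does not die away as n grows, because the true rate lies on the cut-off.
- Going from 19 to 20 procedures raises the pass chance at a true 95% from 0.38 to 0.74 with no change in the procedure, because the first failure becomes permissible.
- Passing a procedure with a true rate of 80% is a small-n problem: 33% at n=5, 11% at n=10, 1% at n=30. A true 90% is separated less well: 35% at n=10 and still 18% at n=30.

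**Benchmark source.** Entry 41 in the reference list is a paper on the analysis of clustered matched-pair data. That fits its use in Section 15.3 for the extended McNemar test, but not its use in Section 15.1 for a biopsy success rate.

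**The case against.** The strongest reply is that little hangs on this rule. It serves an exploratory objective, the biopsy system is described as already 510(k) cleared, and no primary or secondary result, sample size or patient decision depends on the verdict. That stands, and it limits the weight of the point.

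Second, the miss rates above put the true rate exactly at the cut-off, which is the least favourable value for a procedure that meets it. Section 15.1 says only that 95% resembles the stereotactic rate, not that it equals it. This stands in part: at a true 98% the pass chance is at least 0.68, and at 99% at least 0.83, at every n checked. It does not help a procedure that merely matches 95%.

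Third, Section 15.3 already promises frequencies and percentages for categorical measures and leaves room for further analyses, so an interval is not ruled out. True, but none is planned, while the verdict is.

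Three stronger readings are tempting and are not supported:
- *The patient/biopsy switch distorts the result.* Section 15.1 applies the cut-off to patients while the endpoint counts biopsies. However, the study summary foresees one CEM-guided biopsy per participant, in which case the two fractions coincide. The wording needs aligning; the numerical effect is likely small.
- *The verdict depends mainly on how many procedures occur.* At n=20 the pass chance runs from 0.07 at a true 80% to 0.94 at a true 98%, so the true rate matters greatly. Nor is n confined to CEM-only lesions, given the second use in Section 5.4.
- *The procedure is to be declared infeasible below 95%.* The text says when it will be considered feasible. It does not say that this is the only route.

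**Conclusion.** The point holds as a modest one. Applied as an observed proportion, the rule would miss a procedure with a true 95% success rate between 23% and 62% of the time for n from 5 to 83. It would permit no failure up to n=19, and at small n it could pass a weaker procedure. A perfect 10 of 10 would still be compatible with a true rate as low as 69%. A yes/no verdict is therefore not one the data can carry. This rests on the observed-proportion reading and on assumed values of n and the true rate.

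It would be wrong to infer that the rule generally passes poor procedures or fails good ones: by n=30 a true 80% passes only about 1% of the time, and a true 98% or 99% usually passes at any n. The primary accuracy comparison is untouched. The change is worth making because it costs almost nothing.

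**What to change.** In Section 15.1, replace the feasibility sentence with text along these lines:

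> *The number of CEM-guided biopsies and the fraction that adequately sampled the target will be reported per biopsy, with an exact (Clopper-Pearson) 95% confidence interval. A success rate of 95% serves as a descriptive benchmark and not as a pass/fail criterion.*

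This keeps the prespecified 95% in view and aligns the unit with Sections 2.3, 4.3 and 5.5. The citation for the benchmark should also be corrected, since entry 41 is a statistical methods paper.

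The cost is one edited sentence and one reference. The downside is that the sponsor gives up a yes/no claim on an exploratory endpoint. Keeping such a claim would require stating an unacceptable rate and a number of procedures. As illustration only, with exact one-sided error of at most 0.05 and at least 80% power at a true 95%, an assumed unacceptable rate of 80% needs 30 procedures with at least 28 successes (error 0.044, power 0.812). An assumed 90% needs 179 procedures, more than the 83 patients enrolled at one biopsy each. Description is the proportionate choice here.

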### 15.2 Sample size

In two recent studies, the authors reported the accuracies of 78.0% (versus 69.0% for MG) [35] and 79.8% (versus 65.3% for MG) [36], respectively. We utilize these clinical evidences for our sample size justifications. Using a two-sided extended McNemar test with a significance level of 0.05, a sample size of 83 patients provides 80% power to detect an accuracy difference of 12% between the two modalities of CEM and FFDM assuming the discordant of 20%. The method proposed by Wu (2018) was used to calculate the sample size, where the multiple lesions were adjusted via the average number of lesions and the variance that were assumed to be 1.4 and 1, respectively [37]. We further assumed the intracluster correlation of 0.4, and 0.2 for the intracluster correlation of the discordant pairs.

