## **10.0** Local Number of Subjects

10.1 83 subjects

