# 12.0 Withdrawal of Subjects\*

*12.1* The patients may refuse participation at any time for any reason.

12.2 The subjects will be withdrawn from the research without their consent in the following situations:

- The patient has consented to the study but is determined to be ineligible before CEM is completed
- The patient does not complete CEM imaging
- The patient refuses a biopsy or chooses to have a biopsy at an outside *institution*
- In these cases, the patients' research files will be removed and any collected data will not be used for analysis.

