## **19.0 Resources Available**

19.1 A full-field digital mammography system capable of providing lowand high-energy exposures to the breast under the same compression, as well as producing subtracted contrast images, such as Senographe Pristina (GE Healthcare, Buc, FR)

19.2 A CEM- guided biopsy device (GE Healthcare, Buc, FR) is planned to be installed in November 2020

*19.3 %FTE is requested for a dedicated clinical mammography technologist and a clinical study coordinator* 

19.4 Approximately 5-8 patients per day are seen in the multidisciplinary clinic for staging of BC diagnosed at OSF. This results in a minimum of 1,305 potentially eligible patients. Recruiting 6% of the eligible pool, or 2 patients per week will allow completion of recruitment within 12 months.

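### 83 is both the total enrolment and the number said to give 80% power, yet section 12.2 removes patients from analysis with no replacement or allowance

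*Combined protocol and SAP*

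**What the plan says.** Section 15.2 bases the primary comparison, CEM against low-energy images as the equivalent of a standard digital mammogram, on a two-sided extended McNemar test at the 0.05 level. It states that "a sample size of 83 patients provides 80% power to detect an accuracy difference of 12% between the two modalities of CEM and FFDM", with 20% discordance. On clustering it says that "multiple lesions were adjusted via the average number of lesions and the variance that were assumed to be 1.4 and 1, respectively", and adds: "We further assumed the intracluster correlation of 0.4, and 0.2 for the intracluster correlation of the discordant pairs".

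The enrolment figure is the same number. The Study Summary (section 1.0) gives a sample size of 83, section 10.0 reads "10.1 83 subjects", and section 20.0 marks multi-site research as not applicable, so no other site adds patients.

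Section 12.2 lists when a consented woman is withdrawn without her consent: she is found ineligible before CEM is completed, she does not complete CEM, or "The patient refuses a biopsy or chooses to have a biopsy at an outside" institution. For all of these, the "research files will be removed and any collected data will not be used for analysis".

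The document gives no removal rate, replacement rule, over-enrolment or target number of evaluable patients.

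**The concern.** A power statement applies to the patients who reach the analysis. Here the number needed for 80% power equals the number to be enrolled, while another section of the same protocol says that some enrolled women will not be analysed. If even one woman is removed and not replaced, the analysis is smaller than the one that section 15.2 describes.

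The removals are foreseeable, because the protocol lists them and they apply after consent. Having the biopsy at an outside institution is a plausible event in a population defined by referral from outside facilities.

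At stake is how a non-significant primary result would be read. It would be judged against a stated 80% chance of detecting a 12-point difference, when the real chance was lower by an amount that the plan neither estimates nor mentions.

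**Working it through.** **Inputs, all from section 15.2:** two-sided alpha 0.05 (z = 1.96); power 80% (z = 0.8416); accuracy difference d = 0.12; discordant proportion p = 0.20; lesions per patient with mean 1.4 and variance 1; correlations 0.4 and 0.2. The formula in the cited paper is not in the document, so the way the two correlations enter is inferred.

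**Step 1. Lesion pairs needed without clustering.**

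n = [1.96 × √0.20 + 0.8416 × √(0.20 − 0.12²)]² / 0.12² = (0.8765 + 0.3626)² / 0.0144 = 106.6 lesions.

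**Step 2. Reproduce 83.** Patients = 106.6 × design effect / 1.4. Two readings give the plan's figure:

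- Reading A uses the product of the correlations, 0.4 × 0.2 = 0.08, and the variance of 1. Design effect = 1 + [(1.4² + 1)/1.4 − 1] × 0.08 = 1.089. Patients = 82.9.
- Reading B uses a correlation of 0.2 and ignores the variance. Design effect = 1 + (1.4 − 1) × 0.2 = 1.08. Patients = 82.3.

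Both round up to 83, or about 116 lesions (83 × 1.4). Neither contains any allowance for removals.

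**Step 3. Power when fewer than 83 are analysed.** With n_eff = patients × 1.4 / design effect,

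power = Φ[(√n_eff × 0.12 − 1.96 × √0.20) / √(0.20 − 0.12²)].

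The removal rates are assumptions, since the document gives none.

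| Removed (assumed) | Analysed | Power, A | Power, B | Difference detectable with 80% power |
|---|---|---|---|---|
| 0% | 83 | 80.0% | 80.4% | 12.0 points |
| 5% | 79 | 78.0% | 78.4% | 12.2–12.3 points |
| 10% | 75 | 75.8% | 76.2% | about 12.6 points |
| 20% | 66 | 70.2% | 70.6% | about 13.4 points |

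The first removal already takes power just under 80%: at 82 analysed it is 79.5% (A) or 79.9% (B).

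**Step 4. Enrolment needed to analyse 83.** 83/0.95 = 87.4, so 88; 83/0.90 = 92.2, so 93; 83/0.80 = 103.75, so 104.

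**Step 5. Feasibility.** Section 19.4 plans 2 patients per week for 12 months: 2 × 52 = 104.

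**The case against.** The best defence has three parts. First, the document is silent on replacement; it does not forbid it. Participation is a single CEM examination (section 8.1), and two of the three withdrawal reasons operate at or before it. Those women resemble screen failures, and the sponsor may mean 83 as the number who complete. Second, every removal rate above is assumed, and 5% costs only about 2 points of power. Third, 2 per week leaves room for about 21 women beyond 83.

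The second and third parts stand: the loss may be small and is easy to absorb. The first shows a plausible intention, but the text does not express it. Section 10.1 gives 83 subjects with no word on evaluability, and the biopsy reason can apply after CEM is done.

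Three stronger readings are tempting and are not supported.

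- *That 83 is miscalculated.* Other ways of combining the correlations give different totals. Two plausible ones give 83, and without the cited formula no error can be shown.
- *That section 19.4 contradicts the target.* It says "This results in a minimum of 1,305 potentially eligible patients", and 6% of 1,305 is 78. But 83/1,305 = 6.36%, which rounds to 6%, and 83/52 = 1.6 per week, which rounds to 2. Both are rounded descriptions of recruiting 83.
- *That the mean of 1.4 includes the index cancer.* Only 0.4 additional sites per woman would then remain, and power under Reading A would be about 30%. Section 15.2 does not say which lesions it counts. However, sections 1.0, 4.1 and 15.1 direct the primary analysis to additional sites (section 4.1: "up to 4 additional biopsy sites will be included in the analysis"), so the natural reading is that 1.4 refers to those. This is missing detail, not a demonstrated fault.

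**Conclusion.** The concern holds as an inconsistency between the power statement and the plan's own enrolment and exclusion rules. The 80% in section 15.2 reproduces, but only if all 83 enrolled women are analysed, and section 12.2 anticipates that some will not be.

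The size depends on a removal rate that the plan does not give: about 2 points of power lost at 5%, 4 at 10% and 10 at 20%. These figures rest on Readings A and B, on the section 15.2 inputs being right, and on removed women not being replaced, which is inferred from silence. This should be corrected, but it does not undermine the design.

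**What to change.** In sections 10.1 and 15.2, choose one of two statements.

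1. Keep enrolment at 83, state the number expected to be analysed after section 12.2 removals with the reason for that rate, and give the power or detectable difference for that number. The cost is wording and a slightly lower stated power.
2. State that 83 is the number analysed and that women removed under section 12.2 are replaced until 83 are analysed, with the enrolment ceiling in sections 1.0 and 10.1 raised to match. The cost is about 5, 10 or 21 more women at 5%, 10% or 20% removal (88, 93 or 104 enrolled). All three fit 12 months at 2 per week, the last with nothing to spare.

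As a minor clarification in section 15.2, say that 1.4 is the mean number of additional sites per analysed woman, with the index lesion excluded and women who have none counted as zero. If that is not what 1.4 means, recompute the sample size.
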